### **9.3 Sample Size Estimate**

The power analysis was completed for the primary outcome measure, which is the proportion of daily cigarettes smoked during the 4-hour post-methadone-dosing period. The power calculation was based on data from Richter et al. who evaluated the proportion of daily cigarettes smoked in the 2 - 4 hours post-methadone-dosing. These investigators reported a standard deviation of .135 for the proportion of daily cigarettes smoked during the 2 hour post-methadone-dosing period. The present trial will be evaluating a 4 hour period and, to be conservative, we assumed a standard deviation of .27 for the power analysis.

Assuming a two-sided test, an alpha of .05, and a within-subject correlation of .80, a sample size of 20 will provide 78% power to detect a mean difference of .11, which corresponds to a Cohen's d of .41, as statistically significant. In the present study, eligible participants will, during baseline, use at least .30 of their daily cigarettes during the 4-hour post-methadone-dosing period; for a participant using .30 during baseline, a reduction to .19 or lower would be in the range of a statistically-significant change. Based on the eligibility criteria and the fact that we are utilizing M-M patients, who have a very high rate of retention, we are assuming that all 20 randomized participants will complete the study. If only 18 of the participants complete the study, using the assumptions outlined above, we would have 78% power to detect a mean difference of .12, which corresponds to a Cohen's d of .43, as statistically significant.

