## **6.4 Participant Selection**

### **6.4.1 Inclusion Criteria**

Potential participants must:

1. be male or female, 18 years of age or older
2. be able to understand the study, and having understood, provide written informed consent in English
3. have been enrolled in the UCPC-OTP program for at least 30 days and be stable on the current methadone dose for at least 1 week
4. have smoked cigarettes for at least 3 months, have a measured exhaled CO level  $> 8$  ppm, and not planning to seek smoking-cessation treatment within the next 3 months
5. have a willingness to comply with all study procedures, including trying to stop smoking during designated weeks, and to comply with medication instructions
6. based on a week of Quitbit cigarette lighter assessments, with at least 5 days of useable data, smoke  $\geq 10$  cigarettes/day and smoke at least 30% of daily cigarettes within the 4-hour post-methadone-dosing period
7. if female and of child bearing potential, agree to use one of the following methods of birth control: oral contraceptives, contraceptive patch, barrier (diaphragm or condom), intrauterine contraceptive system, levonorgestrel implant, medroxyprogesterone acetate contraceptive injection, complete abstinence from sexual intercourse, hormonal vaginal contraceptive ring

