### **7.4 Active Treatment Phase**

As outlined in Figure 1, the active treatment phase is 7 weeks in duration. During this time, participants will receive all four medications and will be scheduled for one research visit per week. Participants will be instructed not to smoke during medication evaluation weeks, which are study weeks 1, 2, 4 and 7. During medication evaluation weeks (i.e., Weeks 1, 2, 4, and 7) the research visits will be scheduled to occur during day 6 or 7 of the week in order to maximize participant exposure to the medication/placebo prior to assessment. All assessments ideally will be completed after the participant has received his/her methadone dose and before the participant smokes a cigarette, with the exception of the baseline visit when participants will be allowed to smoke prior to completing the assessments.

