### 9.2 Analysis Plan

All analyses will be completed using SAS, Version 9.3 (SAS Institute, 2010).

1. Primary outcome analysis. The primary outcome analysis will consist of two sets of statistical analyses, one comparing the effect of NNS to PNS on the proportion of daily cigarettes smoked during the 4-hour post-methadone-dosing period and one comparing the effect of varenicline to placebo on the proportion of daily cigarettes smoked during the 4-hour post-methadone-dosing period. The statistical approach taken to both sets of analyses will be the same. A normal mixed model regression will include treatment (active vs. placebo) and the proportion of cigarettes smoked during the post-methadone-dosing period during baseline as covariates. In addition, corrected Akaike Information Criterion (AICC), will be used to determine whether treatment order (see Table 1), time (days 1-7), and / or the treatment-by-time interaction should be included as covariates in the mixed model regression. The dependent variable will be the proportion of daily cigarettes smoked during the 4-hour post-methadone-dosing period from the weeks during which the medication/placebo is being evaluated (see Table 2). The baseline urine drug screen result (positive or negative for substances other than opioids) will be controlled for in the analyses.

2. Secondary outcome analyses. The present trial has six secondary objectives, the analytic approach taken for each is described below. The baseline urine drug screen result (positive or negative for substances other than opioids) will be controlled for in the analyses.

2a. Preliminary evaluation of the ability of the NNS and varenicline, relative to placebos, to reduce total cigarettes per day (CPD). This secondary outcome analysis will consist of two sets of statistical analyses, one comparing the effect of NNS to PNS on CPD and one comparing the effect of varenicline to placebo on CPD. The analytic approach utilized for the primary outcome analysis will be used for this analysis with the variable of interest being CPD (i.e., as opposed to the proportion of daily cigarettes smoked during the post-methadone-dosing period).

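### Does the .30-to-.19 illustration in section 9.3 misstate what a significant result would look like?

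*Combined protocol and SAP*

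**What the plan says.** Section 9.3 (Sample Size Estimate) states its inputs as "Assuming a two-sided test, an alpha of .05, and a within-subject correlation of .80", adds "we assumed a standard deviation of .27 for the power analysis", and concludes that "a within-subject correlation of .80, a sample size of 20 will provide 78% power to detect a mean difference of .11". It then takes .30, the lowest baseline share that eligibility allows, subtracts .11 and writes: "for a participant using .30 during baseline, a reduction to .19 or lower would be in the range of a statistically-significant change".

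Three other places bear on that sentence:

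- Section 9.2 (Analysis Plan) defines the test: "A normal mixed model regression will include treatment (active vs. placebo"), with the baseline proportion entered as a covariate. Each drug is compared with its own placebo, in two separate sets of analyses.
- Section 7.4 (Active Treatment Phase) covers active and placebo evaluation weeks alike: "Participants will be instructed not to smoke during medication evaluation weeks, which are study weeks 1, 2, 4 and 7".
- Section 6.4.1 (Inclusion Criteria) requires that participants "smoke at least 30% of daily cigarettes within the 4-hour post-methadone-dosing period", judged on the baseline week of lighter data.

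**The concern.** The example appears to make three substitutions.

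1. It moves from a mean over 20 people to one participant. One person's change is far noisier than a mean of 20.
2. It moves from the placebo week to baseline. Participants are selected for a high share in the baseline week and are told not to smoke in every evaluation week. The placebo-week mean therefore need not equal the baseline mean, and the plan assumes no value for it.
3. It treats the difference detectable with 78% power as though it marked where significance begins. The boundary for an observed difference is smaller.

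This is the only sentence in section 9.3 that turns the power figure into a result a reader could recognise. A reader who took it literally might judge response by change from baseline, which mixes any drug effect with the instruction to quit and with selection on the baseline week. The placebo weeks are there to remove both. The study is also a pilot meant to inform a larger trial, so a wrong benchmark could be carried forward.

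**Working it through.** **Inputs, all from section 9.3:** SD .27 in each condition, within-subject correlation .80, n = 20, two-sided alpha .05, mean difference .11.

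**Step 1: reproduce the plan's power.** With a paired t-test,

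- SD of the difference = .27 × √(2 × (1 − .80)) = .1708
- standard error = .1708 / √20 = .0382
- noncentrality = .11 / .0382 = 2.88, with 19 degrees of freedom
- power (noncentral t) = 78.0%, and d = .11 / .27 = .41

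Both agree with the plan. For 18 completers, d = .43 means a difference of .43 × .27 = .116, which rounds to the plan's .12; its power is 77.6%, again the stated 78%.

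**Step 2: the sentence as a group illustration.** The smallest observed difference that is significant is 2.093 × .0382 = .080. The plan states no placebo-week mean, so the table sets an active-week mean of .19 against several assumed values.

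| Assumed placebo mean | Difference | t | p |
|---|---|---|---|
| .30 | .11 | 2.88 | .0096 |
| .28 | .09 | 2.36 | .029 |
| .27 | .08 | 2.10 | .0498 |
| .26 | .07 | 1.83 | .083 |
| .25 | .06 | 1.57 | .13 |

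From .30, a mean of .19 or lower is therefore significant, as the sentence says. A mean of .30 − .08 = .22 would be too, so .19 lies inside the significant range and is not its edge.

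**Step 3: how far the .27 cut-off depends on the correlation.** Holding the active mean at .19, the placebo mean needed is .247 at correlation .90, .270 at .80, .288 at .70 and .303 at .60. At .60 the example would just fail, but power for .11 would also have fallen to 49%. That would be a question about the correlation assumption, not about this sentence.

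**Step 4: the sentence as a statement about one person.** The answer depends on a model the plan does not supply.

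- Treat one person's change as a single draw with SD .1708, borrowing the .80 for baseline against a treatment week. Then .11 / .1708 = 0.64 and p = .52. The change needed is 1.96 × .1708 = .335, more than the whole .30.
- Compare seven baseline days with seven treatment days within one person, assuming independent days with SD .27 × √.20 = .121. The standard error is .121 × √(2/7) = .0645. The change needed is .127 (normal) to .141 (t), and a fall from .30 to zero is 4.65 standard errors.

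Under neither model is .11 significant for one person. The shortfall is large in the first and small in the second, and whether a fall to zero would count reverses between them. Neither figure is a property of this plan, because no single-participant test is planned.

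**The case for a change.** The best case for a change is that the words are wrong as written. The sentence names a participant and names baseline, whereas section 9.2 tests a group contrast with placebo. No reading of the plan's inputs that was tried makes .11 significant for one person. The group reading needs a placebo mean of about .27 or more, which is not stated. A correction would cost one line and no patients.

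What stands is the description: the wording is loose and the comparator is misnamed. The rest is weaker.

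- The sentence follows directly from a stated mean difference, subtracts it from the eligibility floor and is hedged as being in a range. A statistician will read it as a group example, and read that way it is true.
- Nothing shows that the placebo-week mean would drop below .27. Everyone enters at .30 or above, so the baseline group mean is at least .30. Regression to the mean is possible, but the documents give nothing from which to size it. The instruction not to smoke reduces both the numerator and the denominator of a proportion, so its effect on the share could go either way.
- Section 9.2 already treats the two drug comparisons as separate. That the 78% applies to each comparison is clear, and no passage requires both to succeed.
- No passage defines a responder or tests change from baseline, so the feared misuse has no route into the trial's results.

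**Conclusion.** No change to the plan is needed. Section 9.3 illustrates a group active-minus-placebo difference of .11 as though it were one participant's fall from baseline. That is a slip of wording in a hedged example. The 78% power is correct on the plan's inputs, the sample size stands, and the primary analysis in section 9.2 makes the right comparison whatever the example says.

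The useful reading is this: with 20 completers, SD .27, correlation .80 and a paired t-test, an observed group difference of about .08 is significant and a true difference of .11 is detected with 78% power. If the placebo-week mean were .30, that .11 corresponds to an active-week mean of .19. These figures approximate the planned mixed model, which adds baseline and urine-screen covariates, and they move with the assumed correlation. An analyst following section 9.2 would reach the same result with or without the sentence.

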## **10.0 Monitoring**

### **10.1 Clinical Monitoring**

Qualified personnel will ensure study procedures are conducted and that study data are generated, documented, and reported in compliance with the protocol, GCP, and applicable regulations.

Study documentation includes all case report forms, data correction forms, workbooks, source documents, monitoring logs and appointment schedules, sponsor-investigator correspondence, and signed protocol and amendments, Ethics Review Committee or Institutional Review Committee correspondence and approved consent form and signed participant consent forms.

Source documents include all recordings of observations or notations of clinical activities and all reports and records necessary for the evaluation and reconstruction of the clinical research study. Whenever possible, the original recording of an observation should be retained as the source document; however, a photocopy is acceptable provided that it is a clear, legible, and exact duplication of the original document.

### **10.2 Confidentiality**

Participant records will be held confidential by the use of study codes for identifying participants on CRFs, secure storage of any documents that have participant identifiers, and secure computing procedures for entering and transferring electronic data.

### **10.3 Safety Monitoring**

#### **10.3.1 Adverse Events (AEs)**

The Investigator may appoint a Study Clinician for this study, who will review or provide consultation for each Serious Adverse Event (SAE) as needed. These reviews will include an assessment of the possible relatedness of the event to the study intervention or other study procedures. The Study Clinician will also provide advice for decisions to exclude, refer, or withdraw participants as required. The study staff will be trained to monitor for and report adverse events and Serious Adverse Events.

#### **Definitions of Adverse Event and Serious Adverse Event**

**Adverse Event:** An **adverse event** (AE) is any untoward medical occurrence in humans, whether or not considered study drug/intervention related which occurs during the conduct of a clinical trial. (Any change from baseline in clinical status, ECGs, routine labs, x-rays, physical examinations, etc., that is considered clinically significant by the study investigator are considered AEs.)

**Suspected adverse reaction** is any adverse event for which there is a reasonable possibility that the study drug/intervention caused the adverse event. A reasonable possibility implies that there is evidence that the study drug/intervention caused the event.

**Adverse reaction** is any adverse event caused by the study drug/intervention.

**Serious Adverse Event (SAE):** A serious adverse event (SAE) refers to all serious events including serious adverse events or serious suspected adverse reaction or serious adverse reaction as determined by the study investigator or the sponsor is any event that results in any of the following outcomes:

1. Death: A death occurring during the study or which comes to the attention of the investigator during the protocol-defined follow-up after the completion of the study, whether or not considered treatment-related, must be reported.
2. Life-threatening AE (Life-threatening means that the study participant was, in the opinion of the investigator or sponsor, at immediate risk of death from the reaction as it occurred and required immediate intervention.)
3. Inpatient hospitalization or prolongation of existing hospitalization
4. Persistent or significant incapacity or substantial disruption of the ability to conduct normal life functions
5. Congenital abnormality or birth defect
6. Important medical event that may not result in one of the above outcomes, but may jeopardize the health of the study participant or require medical or surgical intervention to prevent one of the outcomes listed in the above definition of serious event.

**Unexpected Adverse Event:** Any adverse event, the specificity or severity of which is not consistent with the investigator brochure or the package insert. If neither is available then the protocol and consent are used to determine an unexpected adverse event.

**Pregnancy:** Any pregnancies that occur on study will be captured on a pregnancy CRF and not separately reported as an AE or a serious event. Women who become pregnant during the study period will be discontinued from further study drug/intervention and referred for medical care.

**Medical History:** A thorough medical history during the eligibility assessment phase should record any chronic, acute, or intermittent preexisting or current illnesses, diseases, symptoms, or laboratory signs of the participant, to avoid reporting pre-existing conditions as new AEs and to assist in the assessment of worsening in intensity or severity of these conditions that would indicate an AE. Stable chronic conditions, such as arthritis, which are present prior to clinical trial entry and do not worsen are not considered AEs.

**Eliciting and Reporting Adverse Events:** Appropriately qualified and trained research personnel will elicit participant reporting of AEs and SAEs at each study visit designated to collect AEs. Adverse events (medical and/or psychiatric) assessment will initiate with participant consent and follow-up will continue through 30 days post last study visit. Research personnel will obtain as much information as possible about the reportable AE/SAE to complete the AE/SAE forms and will consult as warranted.

Standard reporting, within 7 days of the site becoming aware of the event, is required for reportable AEs. Expedited reporting (within 24 hours of their occurrence and/or site's knowledge of the event) is required for reportable SAEs (including death and life-threatening events). Reporting of serious events to the IRB will occur per the IRB's guidelines.

Additional information may need to be gathered to evaluate the SAE and to complete the appropriate CRFs. This process may include obtaining hospital discharge reports, medical records, autopsy records or any other type records or information necessary to provide a complete and clear picture of the serious event and events preceding and following the event. If the SAE is not resolved or stabilized at the time of initial reporting or if new information becomes available, follow-up information must be submitted as soon as possible.

Reportable AEs/SAEs will be followed until resolution or stabilization or study end, and any serious and study-related AEs will be followed until resolution or stabilization even beyond the end of the study.

### **Reportable Serious Adverse Events**

For the present study, the following SAEs will not be recorded in the data system nor reported to IRB.

- Admission to a hospital/surgery center for preplanned/elective surgeries;
- Admission to a hospital for scheduled labor and delivery

### **Assessment of Severity and Causality**

The study medical clinician will review reportable AEs and SAEs for seriousness, severity, and causality on at least a weekly basis.

Guideline for Assessing Severity: The severity of an adverse event refers to the intensity of the event.

Grade 1	Mild	Transient or mild discomfort (< 48 hours), no or minimal medical intervention/therapy required, hospitalization not necessary (non-prescription or single-use prescription therapy may be employed to relieve symptoms, e.g., aspirin for simple headache, acetaminophen for post-surgical pain)
Grade 2	Moderate	Mild to moderate limitation in activity some assistance may be needed; no or minimal intervention/therapy required, hospitalization possible.
Grade 3	Severe	Marked limitation in activity, some assistance usually required; medical intervention/ therapy required hospitalization possible.

Guideline for Determining Causality:

The study investigator will use the following question when assessing causality of an adverse event to study drug/intervention where an affirmative answer designates the event as a suspected adverse reaction:

Is there a reasonable possibility that the study drug/intervention caused the event?

**Participant Withdrawal:** The investigator in consensus with a study physician must apply his/her clinical judgment to determine whether or not an adverse event is of sufficient severity to require that the participant be discontinued from study drug/intervention. If necessary, the investigator may suspend any trial treatments and institute the necessary medical therapy to protect a participant from any immediate danger. A participant may also voluntarily withdraw from treatment due to what he/she perceives as an intolerable adverse event or for any other reason. If voluntary withdrawal is requested, the participant should be asked to complete an end of study visit assessment and be referred to appropriate medical care and followed until the symptoms of any adverse event resolve or their condition becomes stable.

### **10.3.2 Protocol Deviation Reporting and Management**

A protocol deviation is any departure from procedures and requirements outlined in the protocol. Protocol departures may occur on two levels, significant versus non-significant. Significant deviations include those that significantly affect the safety of the participant, the safety of the researchers, or the scientific quality of

the study. Non-significant deviations are those that are highly unlikely to impact safety of the participants or scientific integrity of the study. All protocol deviations will be noted and reported to the IRB as required.

## **11.0 DATA MANAGEMENT AND PROCEDURES**

### **11.1 Data Acquisition and Transmission**

All research staff will be trained in Good Clinical Practice (GCP) guidelines. All diagnostic, efficacy and tolerability data collected will be in the form of diagnostic and rating instruments, electronic record from the Quitbit cigarette lighter, and results from laboratory tests. All information collected will be de-identified. Only research staff members that are directly involved with patient care and study procedures will have access to patient identity.

### **11.2 Data Entry and Management**

Most data collected for the current study will be captured first on paper CRFs that will match closely the electronic data entry forms designed to facilitate entry of those data into the database. Entry into the database will be performed by the study research assistants and other study staff members who have been trained to perform this task. After database lock, data will be downloaded to the statistical package being used for data analysis.

